2.1.5 Non-Small Lung Cancer (NSLC)

Metastatic lung cancer is the leading cause of cancer death worldwide with a 5-year survival for advanced disease of less than 5% despite of a comprehensive therapeutic approach. In few tumor types with distinct molecular alterations, unprecedented benefits can be delivered by very specific molecular targeted therapies. For most patients with advanced NSCLC, platinum-based chemotherapy with or without maintenance therapy, and subsequently followed by second-line cytotoxic chemotherapy, is the standard treatment (median survival of approximately 1 year). Second-line cytotoxic therapies (ie, docetaxel, pemetrexed and erlotinib) have only moderate efficacy and are associated with significant toxicities. For this reason, strategies such as immunotherapy, which may have efficacy irrespective of histology or mutational status, are particularly attractive ([Minguet et al, 2015](#); [Garon et al, 2015](#)). Latest approvals (2015) of several immunotherapy agents reflect the scientific progress poised to shape further the patient outcomes in this indication (Garon et al, 2015; [Romero, 2015](#)). As such, anti-PD-1 and anti-PD-L1 antibodies have been shown to produce durable responses in clinical trials in approximately 20% of patients with advanced non-small-cell lung cancer, even without selecting for PD-L1 tumor expression. Pembrolizumab has been recently approved for the treatment of subjects with advanced (metastatic) NSCLC whose disease has progressed after other treatments and have tumors that express PD-L1. In a phase 1 study (KEYNOTE-001) 495 patients received pembrolizumab (at a dose of either 2 mg or 10 mg per kilogram of body weight every 3 weeks or 10 mg per kilogram every 2 weeks) (Garon et al 2015). Among all the patients, the objective response rate was 19.4%, and the median duration of response was 12.5 months. The median duration of progression-free survival was 3.7 months, and the median duration of overall survival was 12.0 months. Among all the patients with a PD-L1 tumor proportion score (TPS) of at least 50%, median progression-free survival was 6.3 months, and the median overall survival was not reached. In a subgroup of these patients (73/313 patients in the validation group with TPS of at least 50%), the response rate was 45.2%. Among the 1143 screened patients, 824 had samples that could be evaluated by the clinical-trial assay, with a prevalence of 23.2% of patients with a PD-L1 TPS of at least 50%, 37.6% with a score of 1 to 49%, and 39.2% with a score of less than 1% by the clinical-trial assay. The prevalence of a proportion score of at least 50% was 24.9% among previously untreated patients and 22.7% among previously treated patients. The ORR in

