3.5 Estimated Study Duration

3.5.1 Study Duration for Subjects

The duration of screening for each subject will be approximately 28 days. The duration of treatment will vary for each subject. Subjects enrolled in Part 1 and 2 of the study can be treated for up to 24 months if treatment is tolerable and clinical benefit is observed. All subjects will complete a safety follow-up visit approximately 135 (+7) days after the last dose of study treatment. After the safety follow-up visit, depending on the duration of their treatment on the study, some subjects will enter the long-term follow-up. The goal of the long-term follow-up is to obtain disease progression and survival information for a period of 12 months after the first combination dose. The actual duration of the study for an individual subject is dependent upon the time required to assess PFS and OS at 12 months.

For subjects who continue treatment past 12 months and up to 24 months (if tolerable and clinical benefit is observed), only Visit Date, IP Administration, and AE/SAE information will be collected in EDC. Remaining follow-up to be performed per institutional standard of care.

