^j Radiographic imaging (CT or MRI) of the chest, abdomen and pelvis, and MRI of the brain if a subject has signs and symptoms suggestive of CNS metastases, are required at screening. MRI of the brain is required for all NSCLC subjects at screening. Tumor assessments must also include all other sites of disease. The screening scans must be done within 28 days prior to enrollment. During treatment, radiographic imaging (CT or MRI) of the chest, abdomen and pelvis, along with tumor assessments of all other sites of disease, (MRI of the brain if a subject has symptoms or signs suggestive of CNS metastases), will be performed independent of treatment cycle at week 10 (± 1 week), and then every 10 weeks (± 2 weeks) or more frequently if clinically indicated until confirmed PD per irRECIST or start of new anticancer treatment. Imaging should not be adjusted for cycle initiation delays and performed according to the calendar. The imaging modality selected (eg, CT or MRI) should remain constant for any individual subject. Response or progression should be confirmed by repeated radiographic imaging ≥ 4 weeks after the first indication of response or progression. Radiographic imaging is required at the safety follow-up visit if the subject ended treatment prior to confirmed PD and has not had radiographic tumor imaging performed within 6 weeks (+1 week) of the visit. The radiographic images will be submitted to a central imaging lab.

^k PK samples should be collected at the exact nominal time point as noted, where collection times are to be defined relative to the end of AMG 820 infusion. If unable to collect a PK sample at the specified nominal time point collect it as close as possible to the nominal time point and record the actual collection time. PK samples not collected at exact nominal time point will not be considered protocol deviations.

^m Safety labs should be performed and reviewed within 2 days prior to each dose.

ⁿ CEA for CRC and CA 19-9 for pancreatic cancer every 6 weeks ± 2 weeks

^o For subjects who discontinued treatment for any reason other than confirmed PD, every effort should be made to perform radiographic imaging (CT or MRI) of the chest, abdomen and pelvis, along with tumor assessments of all other sites of disease every 12 weeks until documentation of confirmed PD per irRECIST, clinical progression, start of new anticancer therapy, or up to 12 months after subject's enrollment for the study, whichever occurs first.

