#### Duration of Response

Duration of response is defined as the number of days between the date of the first tumor assessment indicating an objective response through to the subsequent date of progression as classified by irRECIST or death, or where applicable date of censoring [date of first progressive disease assessment or death or date of censoring – date of the first objective response result +1]. Subjects who respond and have not progressed while on study or died will be censored at the date of the last evaluable radiological assessment. Subjects who do not achieve an objective response will be excluded from the analysis of duration of response.

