#### Investigational Product

The term 'investigational product' is used in to reference to AMG 820 in combination with pembrolizumab.

---

Last Investigational Product Dose Date

The last AMG 820 dose date for each subject is defined as the latest date AMG 820 is administered.

Objective Response as per irRECIST (irOR)

Objective response is defined as a complete response or partial response, as defined by the irRECIST. Confirmation is done by a repeat, consecutive assessment no less than 4 weeks from the date of first documented assessment.

Objective Response Rate as per irRECIST (irORR)

Immune-related ORR (irORR) is defined as the percentage of subjects with irOR.

Overall Survival Time

Overall survival time is calculated as the number of days from the first administration of AMG 820 to death or if applicable censoring [(date of death or censoring – date of first dose of AMG 820 + 1)]. Subjects who withdraw from treatment without withdrawing consent will be followed for survival status up to 12 months.

Subjects who are alive (no record of death) and are lost to follow-up will be censored at the date of last contact.

Progression-Free Survival Time per irRECIST (PFS)

Progression-free survival time is calculated as the number of days from the first administration of AMG 820 to the first assessment of disease progression as per irRECIST or death due to any cause, or if applicable date of censoring (date of progressive disease or death or censoring – first administration of AMG 820 +1).

The following censoring strategies will be used for the progression free survival analysis:

If a subject's disease has not progressed and the subject is alive, progression-free survival time will be censored at the last date they are known to be progression-free (ie, the last evaluable radiological assessment date).

If a subject has no tumor evaluation in the study, progression-free survival time will be censored at the date of the first administration of AMG 820.

Subjects who withdraw consent to participate in the study prior to disease progression will be censored at their last evaluable radiological assessment date.

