**Analysis will be done using local lab data ie, investigator reported.**

### **10.6.2 Secondary Analysis**

The following analyses will be done using secondary efficacy endpoint data **collected using irRECIST** for all subjects treated at the maximum tolerated combination (combining subjects from Part 1 and Part 2).

Using the Kaplan Meier estimate, the PFS at 6 and 12 months and the OS at 6 and 12 months with corresponding 90% CI will be tabulated.

Listings will be produced for all subjects indicating the OS, PFS, TTR, DOR and TTP. Kaplan Meier curves will be presented for OS, PFS, TTR, DOR and TTP with estimates for rates and 80% CI at selected weeks. TTR will also be analyzed excluding subjects that do not achieve an objective response.

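### Duration of response and PFS curves cannot be interpreted past about week 50, because tumor assessments leave the database at month 12 while later deaths can still count as events

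*Protocol*

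**What the plan says.** Protocol 3.5.1 says that subjects "can be treated for up to 24 months if treatment is tolerable and clinical benefit is observed". For those who go past month 12, "only Visit Date, IP Administration, and AE/SAE information will be collected in EDC", and "Remaining follow-up to be performed per institutional standard of care". Protocol Table 5 (footnote j) sets a different course: imaging at week 10 and then "every 10 weeks (± 2 weeks) or more frequently if clinically indicated until confirmed PD per irRECIST or start of new anticancer treatment". Protocol 7.4 repeats this. Neither place has a month-12 limit.

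The SAP takes its efficacy data from investigator reports (10.6.1, 10.6.2). Under its DOR definition in section 6, "Subjects who respond and have not progressed while on study or died will be censored at the date of the last evaluable radiological assessment", and death is an event whenever it occurs. PFS follows the same pattern: if disease "has not progressed and the subject is alive, progression-free survival time will be censored at the last date" of known freedom from progression, meaning the last evaluable scan, while death from any cause is an event with no time limit. SAP 10.6.2 then states: "Kaplan Meier curves will be presented for OS, PFS, TTR, DOR and TTP with estimates for rates and 80% CI at selected weeks". It sets no end point for these curves. SAP 10.10 lists one departure from the protocol, the dropped RECIST 1.1 analysis, and nothing on this.

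**The concern.** Read together, these rules treat the two components of the endpoint differently after month 12. Progression needs a recorded investigator assessment, and none is listed for collection. Death needs only an event record, and AE/SAE collection continues. A subject alive in response at month 20 is therefore sent back to about week 50 as censored, while a subject who dies at month 18 stays at risk until month 18 and is counted there. Whether a subject remains at risk past week 50 depends on whether that subject later dies, so the censoring is informative by construction.

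DOR is a secondary objective and endpoint with no time limit in either document. The subjects affected are those with the longest benefit. Protocol 10.3.4 places the final analysis after all subjects have ended the study, so the late records would be in the data.

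**Working it through.** The plan gives no figure for DOR or PFS beyond 12 months to reproduce. The example below is scaled to Group 3 (Protocol 10.2). That design does reproduce: the sum over x = 4 to 19 of P(X1 = x) × P(X2 ≥ 13 − x), with X1 binomial on 19 and X2 on 36, is 0.8006 at ORR 30% and 0.0477 at 15%, against the stated 80% and 5%. This checks the scaling only.

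**1. Scan calendar.** Scans fall at weeks 10, 20, 30, 40, 50, 60 and so on. At 4.345 weeks per month, 12 months is 52.1 weeks, so the last scheduled scan inside month 12 is week 50 (50 / 4.345 = 11.5 months). The five scans at weeks 60 to 100 fall after it.

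**2. Longest DOR that scans can show.** 50 − 10 = 40 weeks; 40 / 4.345 = 9.2 months. At the edges of the windows (first scan at week 9, last at week 52) it is 43 weeks, or 9.9 months.

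**3. Tail of the curve.** Let S be the Kaplan-Meier value after the last recorded scan, and let k subjects have a recorded death later. Everyone else is censored by about week 50, so k remain at risk. The successive values are S(1 − 1/k), S(1 − 1/k)(1 − 1/(k − 1)), and so on down to 0 at the last death.

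**4. Example (assumed data).** Thirty per cent of 55 is about 16 responders, all first responding at week 10. Two progress at each of weeks 20, 30 and 40, and ten are progression-free at week 50. Then S = 14/16 × 12/14 × 10/12 = 0.625. Late deaths occur at weeks 78, 86 and 95. The comparison assumes scans recorded to week 100 and no late progression.

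| Late deaths | DOR curve under the plan | DOR curve with scans recorded |
|---|---|---|
| 1 | 0 | 0.625 × 9/10 = 0.5625 |
| 2 | 0.3125, 0 | 0.5625, 0.500 |
| 3 | 0.417, 0.208, 0 | 0.5625, 0.500, 0.4375 |

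With one late death, the plan reports a median DOR of 78 − 10 = 68 weeks, set by that death alone. With scans recorded, the median is not reached.

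**5. PFS simulation (assumed model).** n = 55; exponential PFS; 10 to 30% of events are deaths without prior progression; mean 8 months from progression to death; deaths captured to 4.5 months after treatment ends; 1,000 runs per setting. The medians 3.7 and 6.3 months are the pembrolizumab figures in Protocol 2.1.5; 12 months is assumed. In every run with a death after month 12 the curve ended at 0. Mean estimates at month 18:

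| Median PFS (months) | Under the plan | With scans recorded |
|---|---|---|
| 3.7 | 0.044–0.051 | 0.044–0.046 |
| 6.3 | 0.136–0.150 | 0.158–0.164 |
| 12 | 0.293–0.312 | 0.379–0.386 |

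**The case against.** The strongest reply is that the argument reads Protocol 3.5.1 literally for scans but not for deaths. Protocol 9.1.1 and 9.1.3 treat death from the disease under study as a disease-related event, not an SAE, unless it is worse than expected or treatment-related, and 3.5.1 does not list disease-related events. If Protocol 9.2.1 brings them in through the 135-day safety visit, then Table 5 and 7.4 have an equal claim to bring scans in. This stands: capture of disease-related deaths is an inference, and the sections conflict. It does not rescue the curves. If those deaths are not captured, late events are lost instead, and other fatal adverse events still enter as SAEs.

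The documents also work to a 12-month horizon: follow-up in 3.5.1, primary completion in 3.5.2, the later analysis in 10.3.3, and the PFS and OS landmarks. The Amendment 2 rationale says the sponsor has stopped pursuing the combination. That is a fair reason not to demand longer data collection. It is also a reason to end the curves at 12 months, which SAP 10.6.2 does not do.

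A reader might infer three stronger things.

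- *The curves collapse at the first late death.* This holds only if there is exactly one; otherwise the first step is 1/k.
- *Durable responses cannot be measured.* About 40 weeks of response can be.
- *Progression after month 12 leaves no trace.* Progression is a listed reason for stopping treatment (Protocol 8.3.1) and SAP 10.2 summarizes such reasons, although the documents do not say whether this is recorded after month 12.

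Nor is the statement that "the median duration of response was 12.5 months" (Protocol 2.1.5) a general benchmark. It covers all patients in one NSCLC study, and no DOR comparison is planned. Finally, the per-subject listings would let a careful reader spot a lone late death.

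**Conclusion.** The point holds in a limited form. Following the stated rules, the DOR and PFS tails past 12 months are uninterpretable, and scan-observed DOR is capped at about 40 weeks (9.2 months, up to about 9.9 with windows). The numerical effect depends on how many subjects are still progression-free at month 12. For month-18 PFS it is negligible at a 3.7-month median, small at 6.3 months, and about 0.07 to 0.09 at an assumed 12 months.

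ORR, the Simon decisions and the 6-month landmark are unaffected. Twelve-month PFS is largely preserved: the gap between the week-50 scan and month 12 is 52.1 − 50 = 2.1 weeks, and with no death in it the 12-month estimate equals the week-50 one.

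The conclusion rests on two readings: that 3.5.1 governs what is recorded after month 12, and that at least some later deaths reach the database.

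**What to change.** In SAP 6 and 10.6.2, set a cut-off at 12 months from first dose for DOR, PFS and TTP:

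- Progression on or before 12 months is an event; for DOR and PFS, so is death on or before 12 months.
- All other subjects are censored at their last evaluable scan on or before 12 months.
- Later deaths are listed but not counted in DOR or PFS.
- No DOR, PFS or TTP curve or estimate uses follow-up beyond 12 months from first dose.

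Print the number at risk with each landmark, because a death in the short gap between the week-50 scan and month 12 would still meet a thin risk set.

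Separately, reconcile Protocol 3.5.1 with Table 5 (footnote j) and 7.4. If investigator irRECIST assessments are in fact recorded past month 12, use them and move the cut-off to the end of recorded scanning.

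The cut-off costs SAP wording only. Adding tumor assessments to 3.5.1 would be a larger step: it needs a protocol amendment with IRB/IEC approval, and standard-of-care scans need not follow the 10-week schedule or be read by irRECIST. The price of the cut-off is that durability beyond about 9 to 10 months is not estimated, and the report should say so.

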3.5.2 End of Study

Primary Completion: is anticipated to occur when all Study Part 1 and 2 subjects have been enrolled and treated for at least 12 months, been followed up for PFS and OS at 12 months or discontinued from the study.

End of Trial: is when the last subject is assessed or receives an intervention for evaluation in the study. This is anticipated to occur no sooner than when the last subject enrolled in the study has been followed for at least 12 months after the administration of the first combination dose of study treatment.

4. SUBJECT ELIGIBILITY

Investigators will be expected to maintain a screening log of all potential study candidates that includes limited information about the potential candidate (eg, date of screening).

Before any study-specific activities/procedure, the appropriate written informed consent must be obtained (see [Section 11.1](#)). All windows in Inclusion and Exclusion criteria below are relative to first day of study treatment.

4.1 Inclusion Criteria

- 101 Subject has provided informed consent prior to initiation of any study-specific activities/procedures
- 102 Male or female age ≥ 18 years at the time of informed consent
- 103 Pathologically documented, definitively diagnosed, advanced CRC, pancreatic cancer or NSCLC that is refractory to standard treatment, or the subjects have been intolerant to or refuse standard treatment. The select tumor types must also meet the following criteria:
- Part 1 and Group 1: advanced MMR-proficient CRC subjects naïve to anti-PD-1/PD-L1/CSF-1/CSF-1R therapies
 - Part 1 and Group 2: advanced pancreatic cancer subjects with good performance status (defined as ECOG 0-1, good pain management and adequate nutritional intake) naïve to anti-PD-1/PD-L1/CSF-1/CSF-1R therapies
 - Part 1 and Group 3: advanced NSCLC subjects with *low* ($< 50\%$) tumor PD-L1- expression naïve to anti-PD-1/PD-L1/CSF-1/CSF-1R therapies
 - Part 1 and Group 4a: NSCLC subjects with *low* ($< 50\%$) tumor PD-L1-expression who are anti-CSF-1/CSF-1R naïve and have not responded to (disease progression or stable disease > 6 months) or have relapsed during monotherapy with anti-PD-1/PD-L1 therapies
 - Part 1 and Group 4b: NSCLC subjects with *high* ($\geq 50\%$) tumor PD-L1-expression who are anti-CSF-1/CSF-1R naïve and have not responded to (disease progression or stable disease > 6 months) or have relapsed during monotherapy with anti-PD-1/PD-L1 therapies
- 104 Subject must have radiographically and/or clinically measurable disease per RECIST 1.1 ([Eisenhauer et al, 2009](#)). Index lesions must not be chosen from a previously irradiated field unless there has been radiographic tumor progression in that lesion prior to enrollment. See Note: [Appendix D](#) for index lesion and non-index lesion criteria.
- 105 ECOG performance status of 0 - 1
- 106 Adequate organ function determined prior to enrollment, defined as follows:
- Hematological
 - ANC $\geq 1.5 \times 10^9/L$
 - platelet count $\geq 100 \times 10^9/L$
 - hemoglobin ≥ 9 g/dL (without need for hematopoietic growth factor or transfusion support)
 - Renal
 - serum creatinine ≤ 1.5 x upper limit of normal (ULN), OR 24 hr creatinine clearance ≥ 60 mL/min for subject with creatinine levels > 1.5 x ULN.

(Note: Creatinine clearance need not be determined if the baseline serum creatinine is within normal limits. Creatinine clearance should be determined per institutional standard).

- Hepatic
 - serum bilirubin $\leq 1.5 \times \text{ULN}$ OR direct bilirubin $\leq \text{ULN}$ for a subject with total bilirubin level $> 1.5 \times \text{ULN}$
 - aspartate aminotransferase (AST) $\leq 2.5 \times \text{ULN}$ OR $\leq 5 \times \text{ULN}$ for subject with liver metastases
 - alanine aminotransferase (ALT) $\leq 2.5 \times \text{ULN}$ OR $\leq 5 \times \text{ULN}$ for subject with liver metastases
- Coagulation
 - international normalization ratio (INR) or prothrombin time (PT) $\leq 1.5 \times \text{ULN}$, unless the subject is receiving anticoagulant therapy, in which case PT and partial thromboplastin time (PTT)/activated PTT (aPTT) must be within therapeutic range of intended use of anticoagulants
 - PTT or aPTT $\leq 1.5 \times \text{ULN}$ unless the subject is receiving anticoagulant therapy as long as PT and PTT/aPTT is within therapeutic range of intended use of anticoagulants

107 Subjects with NSCLC: Available information regarding recently (within 3 months prior to day 1 and no systemic therapy given since the biopsy) evaluated PD-L1 tumor expression status or willing to provide fresh tumor biopsy to determine eligibility. NSCLC subjects that failed to respond to or relapse during previous anti-PD-1/PD-L1 inhibitors immediately before considering enrolling into current study, may be accepted into the trial based on previously established PD-L1 tumor expression, if discussed and agreed by the Sponsor.

108 Subjects with CRC: Availability of a recent (within 3 months prior to day 1 and no systemic therapy given since the biopsy) and biomarker evaluable tumor tissue sample required at baseline.

109 Subjects with pancreatic cancer: Availability of a recent (within 3 months prior to day 1 and no systemic therapy given since the biopsy) and biomarker evaluable tumor tissue sample required at baseline, whenever feasible.

